1.3 Maxi-K Channels

At least four K channel subtypes are present in human corporal smooth muscle cells. These channels include: (1) the voltage and calcium-sensitive maxi-K, (2) ATP dependent K channels (K_{ATP}), (3) inwardly rectifying channels (Kir), and (4) voltage-gated K channels (Kv).⁷ The primary function of K channels is to modulate Ca^{++} influx through Ca-channels (i.e., L-Type, voltage-dependent). The amount of Ca^{++} that enters the cell through these channels is a major determinant of the free intracellular calcium levels inside the smooth muscle cell, which in turn, determine the degree of smooth muscle cell contraction.

Overall, regulation of the contractile process is organ-specific and modulated by a variety of K channel subtypes.^{16,23-25} The maxi-K channel is the most prominent (numbering approximately 1000 to 1500/cell²²) and well-studied K-channel subtype involved in corporal smooth muscle relaxation. Increased maxi-K channel activity is associated with corporal smooth muscle cell relaxation and penile erection. Moreover, alterations in K channel physiology/function are increasingly being recognized as a major contributing factor to the development of the vascular pathologies associated with diabetes^{17,18} as well as urogenital disorders¹⁴ including erectile dysfunction.^{10,11}

The maxi-K channel is composed of α and β subunits.¹² The α , or pore forming, unit of the maxi-K channel is a tetramer of homologous units. Each α subunit is composed of 11 hydrophobic domains. Seven of the domains are transmembrane spanning (S0-S6) and the remaining 4 domains are cytoplasmic (S7-S10). The α subunit has intrinsic sensitivity to Ca^{++} via the cytoplasmic tail region.²⁵ Even in the absence of the β subunit, expression of the α subunit of the maxi-K channel can form a functional unit; however, expression of the β subunit alone does not form a functional channel.¹⁷ It has been proposed that the role of the β subunit is to modulate the α subunit activity or sensitivity to Ca^{++} .²⁵

1.4 Rationale for Development of *h*Maxi-K

Ion Channel Innovations has developed a gene transfer product, *h*Maxi-K, and plans to investigate the effect of increased expression of maxi-K channels in the smooth muscle of the penis in participants with ED. *h*Maxi-K consists of the gene for the α pore of the maxi-K channel, *h*Slo, inserted into a plasmid vector, pVAX. Because heightened smooth muscle tone may be a causative factor of erectile dysfunction, increased numbers of maxi-K channels following gene expression of *h*Maxi-K may effectively correct ED.^{9,26} This approach to treat ED uses the same principal as drugs developed since 1982, i.e., treatment with medicines causing relaxation of the penile smooth muscle results in rigid erections.

How does Maxi-K channel gene transfer work? The rationale for the utility of K channel gene therapy is related to the important contributions that ion channels make to the contraction and relaxation of smooth muscle cells (i.e., myocytes). Ion channels are membrane proteins that provide a selective permeability barrier to the movement of ions across the cell membrane (influx and efflux of ions, i.e., K^{+} and Ca^{2+} .) In short, these membrane proteins provide a selective channel through which ions can flow (K^{+} flows through K channels, and Ca^{2+} flows through Ca channels, but not vice versa). The opening and closing of these channels is regulated by numerous cellular processes. However, anything that increases the extent that they are open will increase the amount of ion that can move through the channel over any given period of time. The idea behind maxi-K channel gene transfer is to increase the number of maxi-K channels in the cell membrane, so that when the cells are activated by the normal erectile stimulus (i.e., nitric oxide released from nerves), there will be an increase in the efflux of K^{+} from the cell.

The role of the maxi-K channel in generation of an erection can be illustrated by its interaction with nitric oxide (NO) as shown in Figure 2.

[figure not shown]

Figure 2. Interaction of Maxi-K channel and nitric oxide. See text for explanation

The production of NO leads to erection through a pathway that involves cGMP-mediated activation of maxi-K channels resulting in hyperpolarization of vascular and cavernosal smooth muscle cells. As described above, hyperpolarization inhibits the influx of the calcium ion and causes the smooth muscle cells of the corpora to relax allowing increased blood flow into the corpora at systolic pressure and cause erection. Note the central role for protein kinase G (PKG) and ion channels in this pathway and the critical position at the end of the pathway to erection that potassium channel activation has in the erectile mechanism. Thus, loss or erectile function in

diseases associated with a reduction in the expression of the maxi-K channel, in NO release, or in PKG production should be reversed with therapies that increase the number and/or expression of the maxi-K channel. (Modified from Archer ¹¹)

1.5 Description of *hMaxi-K*

The gene for the α or pore-forming subunit, *hSlo*, has been cloned and linked to the kanamycin-resistant plasmid vector, pVAX, to construct *hMaxi-K*. The gene, *hSlo*, is transcribed from the CMV promoter.

Transfection and functional activity of the *hSlo* gene using this vector has been demonstrated in several *in vitro* experiments. In two separate experiments, intracellular uptake and expression of the gene was demonstrated on fluorescence, microscopic, and patch clamp electrophysiological examination of transfected Xenopus oocytes and human embryonic kidney cells.²⁷ Endothelin-1 stimulation causes a transient increase in the intracellular concentration of calcium^{28,29}. A significant decrease was observed in both the resting Ca⁺⁺ levels and the peak amplitude of the ET-1 – induced intracellular Ca⁺⁺ transient in *hSlo*-transfected human corporal smooth muscle cells. Thus, transfer of plasmid-*hSlo* into the smooth muscle cells of the corpora should result in gene expression that allows hyperpolarization of the cells and smooth muscle relaxation with subsequent erection.

The safety and activity of intracorporal injection of varying doses of the *hSlo* gene has been evaluated in 265 aged rats and 256 streptozotocin-induced diabetic rats. The ability of the plasmid-*hSlo* construct to express physiologically functional maxi-K channels has been demonstrated in at least 3 experiments using these two animal models of ED.^{9,26} Animals administered the *hSlo* gene were able to achieve penile rigidity with electrical stimulation of the cavernous nerves.

In order to assay the effect of pcDNA/*hSlo* on the erectile response under conditions that might better mimic natural stimulation for penile erection, two experiments were conducted using either central neural stimulation or apomorphine administration with measurement of the ICP/BP ratio in rats administered a single injection of 100 μ g pcDNA/*hSlo*. In those experiments the medial preoptic area (MPOA) and the paraventricular nucleus (PVN) of the hypothalamus are known to be important to erectile function/capacity in humans and rats.³⁰⁻³³ The drug apomorphine has a higher affinity for D₂-like receptors than other dopamine receptor subtypes (i.e., D1-D5) and it is this receptor subtype that is thought to be the main site for the induction of erections in the paraventricular nucleus of the hypothalamus. Apomorphine is therefore postulated to increase erectile responses by acting as a conditioner in the PVN, increasing the response to sexual stimuli resulting in enhanced erections.

Retired breeder Sprague-Dawley rats were injected intracorporally with 100 μ g pcDNA/*hSlo*. Following electrostimulation of the MPOA, expression of *hSlo* in the rat corporal tissue was confirmed by RT-PCR. Rats injected intracorporally with pcDNA/*hSlo* had significantly higher ICP response compared to untreated age-matched control animals following central stimulation. There was no significant difference in the ICP/BP between the *hSlo*-treated and young control animals following MPOA electrostimulation.

[figure not shown]
In the second experiment, the hypothalamic region involved in erection was stimulated pharmacologically using apomorphine in the retired breeder rat model of erectile dysfunction. Apomorphine acts in the CNS to elicit erectile responses within several minutes of administration. The *hSlo*-treated retired breeder rats received a single intracavernous injection of 100 μ g pcDNA/*hSlo*. Following administration of apomorphine one week later, the *hSlo*-transfected rats had significantly higher ICP/BP ratios than the placebo-treated age-matched

[figure not shown]
control rats.³⁴ Overall, these experiments evaluating the effect of central neural stimulation on the ICP/BP ratio in *hSlo*-treated rats, suggest that expression of *hSlo* and increased maxi-K channels in the membrane of corporal smooth muscle of penis can be responsive to normal physiological mechanisms involved in erection.

[figure not shown]
Although this phase 1 study is designed to evaluate a single administration of *hMaxi-K*, the safety of *hMaxi-K* following multiple administrations has also been investigated in preclinical studies. Doses of *hMaxi-K* evaluated were 10, 30, 100, 300, and 1000 µg. Histopathological examination of the major organs (heart, lung, liver, spleen, kidney, brain, and testes) demonstrated normal tissues among all treatment groups. Importantly, no cardiac toxicity was detected in any animal at any dose of *hMaxi-K*. Laboratory parameters were within normal limits at all timepoints for all doses tested. No adverse clinical effects were seen in cardiovascular parameters.

Extensive biodistribution studies at the ten-copy level of *hMaxi-K* have been conducted in rats administered 1000 µg of intracavernous *hMaxi-K*. Fourteen organs were examined at 1, 4, 8, and 24 hours and 1, 2, and 4 weeks after transfer. Importantly, no signal of gene transfer was detected at any time point in either cardiac myocytes or testis tissue following administration of *hMaxi-K*. In a separate study, the half-life of *hMaxi-K* in human blood was found to be less than 30 minutes. Given the results of the biodistribution studies, the known half-life of *hMaxi-K*, and the proposed use of a penile tourniquet, the amount of *hMaxi-K* able to access the systemic circulation is expected to be negligible.

1.6 Clinical Data

2.0 Objectives

The primary objective of this study is to evaluate the safety of a single intracavernous injection of *h*Maxi-K (either 8,000 or 16,000 µg) compared to placebo in males with erectile dysfunction longer than six months that was attributable to an underlying, stable medical condition upon penile rigidity or erection in males with erectile dysfunction longer than six months that is attributable to underlying, stable medical condition.

The secondary objective of this study is to evaluate the efficacy of a single intracavernous injection of *h*Maxi-K, either 8,000 or 16,000 µg, compared to placebo.

3.0 Study Design

This study is double-blind, placebo controlled parallel design Phase 2A trial evaluating the potential activity and safety of two different doses of *h*Maxi-K (16000 µg, and 8000 µg) given in a single administration relative to placebo injected into the corpus cavernosum of the penis.

The proposed study period is approximately 6 months following the single injection of study drug

per participant. This study will enroll 11 participants at *h*Maxi-K doses of 8000 µg, 11 participants at *h*Maxi-K doses of 16000 µg and 13 on placebo. A maximum of 35 participants will be enrolled.

4.0 Study Population

The study population includes men with erectile dysfunction attributable to an underlying, stable medical condition but who are otherwise in good health. The most common stable medical diseases that cause erectile dysfunction include hypertension and atherosclerosis, antihypertensive medication, type I and type II diabetes mellitus, pelvic surgery and pelvic radiation, cerebrovascular accidents (stroke), multiple sclerosis, and Parkinson's disease. Men with erectile dysfunction secondary to aging as a solitary cause will not be included in the trial.

The target population is men with erectile dysfunction who have been unable to tolerate, do not wish to continue, or have had unsuccessful results with, prior therapy for ED.

Only participants considered eligible according to the protocol-specified eligibility criteria will be able to receive study drug.

4.1 Inclusion Criteria

Eligible participants must meet the following inclusion criteria:

- a) Signed Informed Consent
- b) Be adult males over 18 years of age diagnosed with erectile dysfunction and whose ED is attributable to an underlying, stable medical condition such as hypertension and

atherosclerosis, antihypertensive medication, type I and type II diabetes mellitus, pelvic surgery and pelvic radiation, cerebrovascular accidents (stroke), multiple sclerosis, and Parkinson's disease;

- c) Participants must have been unable to have successful sexual intercourse for 3 months prior to study entry without specific ED therapy such as Vacuum Erection device (VED), Viagra™ (sildenafil), Cialis™ (tadalafil), Muse™ (alprostadiol), or intracavernous injection therapy with an erectile function domain score of IIEF >10 and < 21 at screening and baseline;
- d) Have been unable to tolerate, do not wish to continue, or have had unsuccessful results with, prior therapy for ED, e.g., Viagra™, intracavernous injection therapy, Muse™, or VED;
- e) If diabetic, documentation of HgA_{1c} less than or equal to 8.5 % prior to enrollment;
- f) If receiving medication for hypertension, documentation of blood pressure has been stable on the same medication for at least 2 months prior to enrollment;
- g) Be heterosexual and in a stable, monogamous relationship of at least six months duration;
- h) Agree to attempt intercourse with their partner at least four times per month while participating in the study;
- i) Agree not to use other treatments for ED while participating in this study;
- k) Have screening laboratory values and ECG that are within the normal range. See exclusion criterion below.
- l) Have a normal physical examination of the penis;
- m) If participant had a radical prostatectomy a PSA <0.4 for at least one year documented by 2 measurements during the preceding year;
- n) Be literate, able to give written informed consent, and comply with all study procedures and requirements.

4.2 Exclusion Criteria

Participants will be excluded who have:

- a) A history of sickle-cell disease, sickle cell trait, or any other medical condition that, in the judgment of the investigator, would contraindicate the administration of study medication or interfere with the study evaluations;
- b) In the judgment of the investigator any condition that would interfere with participation in the study (including geographical inaccessibility), that would contraindicate the administration of study medication or interfere with the study evaluations.
- c) Had within six months prior to enrollment any of the following:
 - Myocardial infarction
 - Cerebrovascular accident
 - Uncontrolled hypertension (systolic >160 or diastolic >100mmHg)
 - Arrhythmia
 - Congestive heart failure (dyspnea on minimal exertion or while supine)

- Unstable angina (chest pain greater than three times weekly while on therapy)
- Required treatment with calcium channel, beta-blocker medication/nitrates, or anti-epileptic drugs for less than 6 months at the time of randomization

d) Poorly controlled diabetes mellitus as defined by HgA_{1c} > 8.5 mg% at time of enrollment;

e) Change in medication for diabetes or hypertension within 2 months of study enrollment;

f) Gonadal failure (testosterone < 200 ng/dl) not treated with hormone replacement;

g) History of malignancy except non-melanomatous skin cancers

h) A life expectancy of less than 12 months;

i) An indwelling urethral catheter;

j) A prior penile prosthetic implant

l) Received an investigational drug, investigational therapy, or other form of ED therapy, including approved treatments, within the past 30 days;

m) Peyronie's disease;

n) Any screening laboratory values outside of the normal laboratory range as defined by the central laboratory normal ranges and in the judgment of the investigator is considered clinically significant (hepatic biochemical markers [AST, ALT, GGT, alkaline phosphatase, and bilirubin] > twice the upper limit of the normal reference range may be accepted with written consent of the sponsor).

o) Any clinically significant ECG abnormality

NOTE: Sinus bradycardia of 50-59 bpm is permissible. Other abnormalities that can be normal variants (and considered clinically insignificant) may be permissible. However, participants with such abnormalities cannot be randomized without review of their medical history and prior written approval of the sponsor (or designee).

5.0 Test Material and Administration

5.1 Study Medication

*h*Maxi-K is a double stranded naked plasmid DNA molecule carrying the human cDNA encoding the gene for the α , or pore forming, subunit of the human smooth muscle Maxi-K channel, *hSlo*. Expression of the *hSlo* gene is under control of the CMV promoter positioned upstream of the transgene and the construct also contains the Bovine Growth Hormone poly A site.

Table A below provides information on the dosing of h Maxi-K dosing 8000 μ g, 16000 μ g and placebo. Each 2 mL vial contains 4000 μ g per mL. The sites will store the participant vials at -20°C in a locked freezer prior to use. Vials can be kept at -20°C for up to 360 days. Participant vials will be retained at the site until study completion and after the drug accounting processes have been completed, when they will either be returned to the Sponsor or destroyed with Sponsor approval.

Table 1. - Final Dose – *h*Maxi-K

	8000 µg	16000 µg	PBS-20% sucrose
h Maxi-K	2 ml	4 ml	0 ml
PBS-20% sucrose	2 ml	0 ml	4 ml
Number of Vials*	2	2	2

*Each vial contains 4000 µg per mL.

5.1.1 Packaging and Labeling

Each assigned vial will have a double blinded 2 part detachable label (tear off part to be placed in the participant's source documents). Each vial label will contain the following information:

- Study ION 04-ED
- Participant identification number
- INSTRUCTIONS: Inject contents of both vials into corpora cavernosa
- Store at controlled room temperature once constituted: [REDACTED] C to [REDACTED] C [REDACTED] F to [REDACTED] F).
- CAUTION: New Drug – Limited to investigational use
- Manufactured for Ion Channel Innovations, LLC by Althea Technologies, Inc., San Diego, CA 92121

Note: In each dosing arm, 11 participants will receive *h*Maxi-K and 13 will receive PBS-20% sucrose (placebo).

Sharp Clinical Services, Inc. will prepare 40 kits of product using randomization schedule generated by a Statistical Group. The kits will be shipped to the central pharmacy at Dasman and stored at -20C. Following notification by the site that an eligible participant is to be given the study medication the pharmacy will send the blinded kit to the investigator for use.

The individual participants' double blind patient drug kit will contain a two-part (tear-off) label. The duplicate portion of this label will be detached and affixed to a label page (to be retrieved at study close out by Ion Channel Innovations designated monitor) at the time of randomization and test drug administration. There will be central randomization. The site will be instructed to call the Sponsor or designee for the assigned subject number after each participant's screening visit allowing ample time prior to Visit 2 for shipment of the drug.

The duplicate label from each patient drug kit will be affixed to a separate log in the source documents at Visit 2.

5.2 Dose Selection and Administration

Two doses of *h*Maxi-K will be evaluated: 8,000 µg and 16,000 µg compared to PBS-20% sucrose (control group).

The gene product or PBS-20% sucrose will be administered in the office. The blinded participant kit will be taken from the freezer and the vials warmed to room temperature. The rubber cap of the vial will be wiped with alcohol. The 8 ml contents of the 2 vials (4 ml each) in the kit will be drawn into an 10 ml syringe and administered by the investigator through a 25 gauge needle into the corpora of each participant.

The investigator's pharmacy or a designee will be responsible for dispensing the drug in a timely fashion for use on the day of the participant's Visit 2 and accounting of all drug provided by the sponsor. Records of document control numbers and dates received will be kept on a Drug Inventory Form provided by the sponsor for accounting purposes. Under no circumstances will the investigator supply study drug to other investigators, allow study drug to be used other than directed by this protocol, or destroy or dispose of study drug in any other manner without prior written authorization from the sponsor.

All partially used clinical trial kits will be accounted for and destroyed at the investigative site according to IBC guidance. The investigator or designee, upon completion of the drug accounting process, will send all unused clinical materials back to the Sponsor or designee for disposition.

The investigator or designee will administer study drug and be responsible for the accounting of all drug provided by the sponsor. Records of document control numbers and dates received will be kept on a Drug Inventory Form provided by the sponsor or designee. Under no circumstances will the investigator supply study drug to other investigators, allow study drug to be used other than directed by this protocol, or destroy or dispose of study drug in any other manner without prior authorization from the sponsor. In the event that study drug is only partially administered (e.g., an adverse event occurs during injection), then any partially used vials must be retained for drug accountability. After the Sponsor's designee has completed the drug accountability and approval for drug disposal, study drug may be disposed using the site's standard operating procedure for biohazard waste.

If a clinically serious sign or symptom is reported the medical monitor will contact the sponsor and no further enrollment will be done until the medical monitor or sponsor gives permission. In the previously completed clinical study evaluating intracorporal administration of up to 16000 μg *hMaxi-K* in 20 participants with ED, there was only one adverse event considered possibly related to *hMaxi-K* ("tingling warmth in the glans").

To minimize the possibility of dehydration and/or a vasovagal response following injection of the *hMaxi-K*, participants will be instructed to eat breakfast and drink fluids on that morning.

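### The protocol gives the injected volume as 4 mL in section 5.1 and Table 1 but 8 mL in section 5.2; vial fill and concentration need confirming before further dosing

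*Protocol*

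**What the plan says.** Protocol section 5.1 gives the vial size and strength together: "Each 2 mL vial contains 4000" µg per mL. Table 1, in the same section, allots two vials to every participant and lists these volumes:

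| | 8,000 µg arm | 16,000 µg arm | Placebo |
|---|---|---|---|
| hMaxi-K | 2 mL | 4 mL | 0 mL |
| PBS-20% sucrose | 2 mL | 0 mL | 4 mL |
| Vials | 2 | 2 | 2 |

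Protocol section 5.2 opens by naming the same two doses. It then describes the injection: "The 8 ml contents of the 2 vials (4 ml each) in the kit will be drawn into an 10 ml syringe", to be given through a 25 gauge needle.

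The vial label in section 5.1.1 carries no volume: "INSTRUCTIONS: Inject contents of both vials into corpora cavernosa". A vendor "will prepare 40 kits of product using randomization schedule generated by a Statistical Group", and the kits reach the investigator blinded. The SAP's compliance listing covers treatment, date and whether treatment was administered, but not the volume injected. No other section of either document reconciles the two volumes.

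**The concern.** Section 3.0 describes a product "given in a single administration relative to placebo injected into the corpus cavernosum of the penis", so each participant is dosed once and a wrong dose cannot be corrected at a later visit. The kit is blinded and both vials are injected whole. The dose is therefore set by what the vendor put in the vials, not by anything the investigator can see or adjust. The two sections that describe those vials disagree on how much each one holds.

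If the kits follow section 5.1, participants receive the assigned dose, and the investigator is left with an instruction that cannot be carried out because 8 mL is not there to draw. If the kits follow section 5.2, the dose depends on a concentration that the protocol states only for a 2 mL vial. One combination, 4 mL per vial at 4000 µg/mL, would double the dose in both active arms. Sections 5.2 and 5.2.1 cite earlier human exposure only up to 16,000 µg.

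**Working it through.** **Inputs**
- Vial size 2 mL and concentration 4000 µg/mL: Protocol 5.1.
- hMaxi-K volumes 2, 4 and 0 mL; diluent volumes 2, 0 and 4 mL; two vials per participant: Protocol Table 1.
- Assigned doses 8,000 and 16,000 µg: Protocol 3.0 and 5.2.
- Total volume 8 mL, as two vials of 4 mL: Protocol 5.2.
- Highest earlier human dose cited, 16,000 µg: Protocol 5.2 and 5.2.1.

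**Formulas**
Total volume = vials × fill per vial. Dose = volume of hMaxi-K × concentration.

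**Step 1: reproduce the assigned doses from section 5.1 and Table 1**
- Vials: 2 × 2 mL = 4 mL.
- Table 1 columns: 2 + 2 = 4; 4 + 0 = 4; 0 + 4 = 4 mL.
- Low dose: 2 mL × 4000 = 8,000 µg.
- High dose: 4 mL × 4000 = 16,000 µg.

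Both doses come out exactly. The 4 mL total is not written anywhere, but vial count times vial size and the column sums both give it.

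**Step 2: the volume in section 5.2**
2 × 4 mL = 8 mL, and 8 / 4 = 2. Section 5.2 calls for twice the volume in all three arms.

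**Step 3: can 8 mL be made to fit?**
Half of the low-dose volume is diluent in Table 1. Keeping that proportion, 8 mL contains 4 mL of hMaxi-K in the low arm and 8 mL in the high arm.

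| Reading | Low arm | High arm | Conflicts with |
|---|---|---|---|
| Table 1 as totals per participant, 4 mL at 4000 µg/mL | 2 × 4000 = 8,000 µg | 4 × 4000 = 16,000 µg | Volume in 5.2 |
| 8 mL at 4000 µg/mL | 4 × 4000 = 16,000 µg | 8 × 4000 = 32,000 µg | Assigned doses, 2 mL vial, Table 1 volumes |
| Table 1 as the content of each vial, times two | 2 × 2 × 4000 = 16,000 µg | 2 × 4 × 4000 = 32,000 µg | Assigned doses, 2 mL vial |
| 8 mL at the concentration that keeps the doses | 8,000 / 4 = 2000 µg/mL | 16,000 / 8 = 2000 µg/mL | Stated 4000 µg/mL, 2 mL vial, Table 1 volumes |

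No row satisfies the stated volumes, concentration and doses together. The two rows that combine 8 mL with 4000 µg/mL double both arms: 16,000 / 8,000 = 2 and 32,000 / 16,000 = 2. The high arm would then be at twice the 16,000 µg cited from earlier human use, and the low arm would receive the intended high dose.

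**The case against.** The strongest reply is that this is probably a slip in one sentence. Section 5.1 and Table 1 agree with each other and reproduce both doses. The site injects whole vials, so a wrong volume in section 5.2 would not by itself change what anyone receives. The doubling case contradicts the vial size, the Table 1 volumes and the assigned doses, and no document shows such a fill.

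Much of that stands. Correct dosing with faulty text in section 5.2 is the likeliest state of affairs. It is not certain, however. The figures in section 5.2 (8 mL, 4 mL per vial, a 10 mL syringe) fit one another, so the sentence is more than a single mistyped digit. An 8 mL presentation at 2000 µg/mL would also deliver the right doses. The text cannot settle the matter, so the contents of the vials have to be checked before any wording is changed.

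Three other inferences should be resisted:
- A reader might infer that participants were or will be overdosed. The documents do not support that: the doubled doses follow only from a fill that neither document describes.
- A reader might think the used vials will answer the question, because "Participant vials will be retained at the site until study completion". An emptied vial may show container size but not fill volume or concentration.
- A reader might take two nearby slips as evidence of which section is wrong. Section 5.1 announces a Table A above a table numbered 1 ("Table A below provides information on the dosing of h Maxi-K dosing 8000"), and the table footnote, "Each vial contains 4000" µg per mL, cannot be true of placebo vials. Both are minor, and both lie in section 5.1, so they do not show that section 5.2 is the faulty one.

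**Conclusion.** The inconsistency is real and the dosing text is wrong as written. Section 5.1 with Table 1 implies 4 mL and section 5.2 states 8 mL, a twofold difference in volume in every arm. The assigned doses are met by 4 mL at 4000 µg/mL or by 8 mL at 2000 µg/mL. At 8 mL and 4000 µg/mL they would be 16,000 and 32,000 µg.

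The 4 mL figure rests on Table 1 being totals per participant, which is the only reading that gives the assigned doses at the stated concentration. The doubled figures assume the Table 1 proportions carry over to a larger fill. The actual fill is unknown from the documents, so the consequence is conditional. Sample size, alpha and power are not affected. The point must be fixed because it concerns the operative instruction for a single gene-transfer injection, and the case not yet excluded is a twofold overdose.

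**What to change.** Before further dosing, have unblinded staff confirm vial fill volume and hMaxi-K concentration from the lot-level manufacturing records. Checking the 40 randomized kits one by one at the site would reveal allocation, so the check should stay at lot level and away from blinded personnel. The action then depends on the result:

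- **2 mL at 4000 µg/mL:** correct section 5.2 to a total of 4 ml, from two vials of 2 ml each.
- **4 mL at 2000 µg/mL:** correct the vial size, concentration and volumes in section 5.1 and Table 1.
- **4 mL at 4000 µg/mL:** do not edit the text to match, since that would write a doubled dose into the protocol. Hold dosing, replace the kits, and review the safety of anyone already dosed.

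In the first two cases the cost is one records check and a short protocol amendment with its usual submission (Protocol 12.2.2). There are no added participants, procedures or changes to the analysis. The third case would also cost new kits and a pause in dosing.
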